4. STUDY DESIGN AND PLAN

4.1. Overall Plan

This is an open-label, global multicenter, dose-escalation phase 1 study of 3D185 monotherapy in subjects with advanced solid tumors.

The starting dose in this dose-escalation study is 25 mg, and the preset 7 dose-escalation cohorts are 25 mg, 50 mg, 100 mg, 150 mg, 200 mg, 250 mg, and 300 mg, respectively. This study adopts a combination of accelerated titration and i3+3^[1] for dose escalation. All subjects in each cohort will receive a single oral dose of 3D185, followed by a 7-day washout period (i.e. single-dose PK study period). Then, subjects will receive consecutive daily doses (QD, 28 days/cycle) until disease progression, death, unacceptable toxicity, or withdraw of informed consent, whichever comes first. The DLT evaluation period includes the single-dose PK study period and the first treatment cycle (within 35 days after the first dose). The enrolled subjects will be sequentially assigned to the planned dose cohorts according to the protocol, and receive 3D185 treatment to observe the occurrence of DLT:

Accelerated titration dose-escalation phase: One subject is to be enrolled sequentially to 25 mg and 50 mg cohorts, respectively. If no Grade ≥ 2 drug-related AE occurs during DLT evaluation period, the study will escalate to the next dose level. Otherwise, 2 additional subjects will be enrolled, and the subsequent study will convert to i3+3 dose-escalation design from this dose cohort.

In the accelerated titration phase, a subject may be replaced if he/she 1) does not reach to 75% of the total planned dose; 2) discontinued investigational product due to non-DLT reasons during the DLT evaluation period.

i3+3 dose-escalation phase: Starting at 100 mg cohort, 3 subjects are to be enrolled initially at each subsequent dose cohorts in accordance to i3+3 dose-escalation design. Each dose cohort should recruit at least one subject from each country after sites in both countries are activated. If a cohort requires ≥ 6 subjects, it must enroll at least 1 subject from each country and efforts will be made to ensure number of subjects enrolled from each country is similar.

After 3 subjects in each cohort completed DLT evaluation, the safety monitoring committee (SMC) will review all available safety and PK/PD data from all treated subjects (DLT evaluable and non-DLT evaluable subjects), taking into consideration the dose-assignment recommendation based on i3+3 decision rule (Figure 1; Section 4.2), to make the recommendation on the conduct of the study including the dose level for subsequent subjects. In addition, the SMC will review and evaluate all available safety data if one of the following criteria is met:

- More than 30% of all subjects who received 3D185 experienced serious adverse events (exclude unrelated events assessed by investigator);
- Any investigational product toxicity related death is reported.

Enrollment will be paused while SMC is reviewing the data until a formal decision is made by SMC. The recommendations made by SMC include the following:

- Recommend to start enrollment to the next higher dose level per protocol;
- Recommend to enroll more subjects at a given dose level;
- Recommend whether a lower dose or a different schedule should be evaluated;
- Recommend whether the study should be terminated;
- Recommend to modify the study design

Details of the safety monitoring process will be specified in a dedicated SMC charter.

If a Grade ≥ 2 drug-related AE occurs during the accelerated titration dose-escalation phase, the i3+3 dose-escalation phase will be initiated earlier. If the i3+3 dose-escalation phase starts from 100 mg, the maximum sample size in this phase will be 30 subjects; and, if i3+3 design starts at the dose of 50 mg or 25 mg, the maximum sample size will be 36 or 42, respectively.

If a subject terminates treatment due to non-DLT reasons during the first treatment cycle, there is no need to replace the subject. When the study has increased to a dose level (d) that is beyond the MTD, and according to the i3+3 decision table (Figure 1), the dose-assignment recommendations in cohorts of d and d-1 are dose de-escalation (D) and escalation (E), respectively, a new cohort may be added between the d and d-1 dose cohort after SMC review and evaluation on the available clinical data of PK/PD, safety, and efficacy, the new cohort can be an intermediate dose cohort (25 mg increment/decrement) or an intermittent schedule (such as 3 weeks on, 1 week off; 5 days on, 2 days off, etc.). The sample size will be increased by 6 subjects accordingly.

At the end of the study, the MTD will be inferred based on the DLT data and all safety data observed at all dose levels. The specific MTD estimation method is shown in Section 4.2. The RPTD will be established by taking into consideration of the PK and/or PD profiles and safety data from the dose escalation phase.

The DLT evaluable subject is defined as the subject who received at least 75% of the planned doses of treatment and completed the safety assessment during DLT evaluation period.

During the DLT evaluation period, Subject can withhold 3D185 due to drug-related AEs. If the withholding time is more than 7 days, the AE will be considered as DLT. The subject's dose of 3D185 will not be reduced unless DLT occurs.

4.2. i3+3 Design

Similar to the 3+3 design^[18], the i3+3 is rule-based design, and it is also an interval-based design similar to mTPI^[19]. The specific algorithm of i3+3 design is shown in Appendix 7. Compared to the 3+3 design, the i3+3 design offers greater flexibility (e.g., flexible handling of subject, shedding), higher MTD selection probabilities, and better safety (see Appendix 8 for the comparison results of the simulation trials for 3+3 and i3+3). The target toxicity probability of the MTD in this study is set to pT = 25%, and the equivalence interval (EI) is (16%, 30%). This means

that the MTD should have a toxicity probability near 25% but not below 16% or above 30%. The decision table for the i3+3 design of this study is shown in Figure 1.

[figure not shown]

Figure 1 i3+3 Dose Escalation Decision Table

Note:

This is a decision table for the 3D185 dose-finding study. The target toxicity probability (pT) is 25% and the equivalence interval (EI) is (16%, 30%) for 42 subjects. Each column represents (n) number of DLT evaluable subjects treated at the current dose and each row represents (x) number of subjects with DLTs at the dose level. Each cell in the table provides the dose-assignment recommendation based on the readouts from the corresponding row (x) and column (n). The letters in the decision table represent different dose-assignment recommendations.

The i3+3 dose-escalation phase is expected to enroll 30-42 subjects (maximum sample size will be adjusted according to the first dose entering the i3+3 phase. For details, see Section 4.1). Every 3 subjects as a cohort will be sequentially enrolled.

The specific operation process of i3+3 design is as follows:

- ♦ Three subjects will be enrolled in a cohort to receive the planned dose of 3D185. When i3+3 dose-escalation phase starts, if there is no Grade ≥ 2 drug-related AE occurs during the accelerated titration phase, the subjects in the first cohort in this phase will receive 100 mg 3D185. Otherwise, one of the subjects from the accelerated titration dose-escalation cohort will be enrolled in the first cohort of the i3+3 phase. And 2 additional subjects will be enrolled in this first cohort.
- After the three subjects in each cohort complete the DLT evaluation, the dose-assignment recommendation for the next cohort will be determined according to the decision table (Figure 1) by using the safety data from the DLT evaluable subjects.
 - 1) In Figure 1, "E" stands for escalating to the next higher dose; "S" stands for staying at the current dose; "D" stands for de-escalating to the previous lower dose.
 - 2) "DU" indicates that the toxicity at the current dose level is too high. Thence, it stands for de-escalating to the previous lower dose and marking the current and the higher doses as unacceptable so that it will never be used again in the remainder of the trial to avoid other subjects receiving treatment at these doses to ensure their safety. If the current dose is the lowest dose and the dose-assignment recommendation is "DU", the study should be terminated to ensure the safety and no dose level will be selected as the MTD.
 - 3) If the current dose is the lowest dose and the dose-assignment recommendation is "D", the study will continue to enroll new subjects at the current dose. Once the dose-assignment recommendation is "DU", the study should be terminated to ensure safety.
 - 4) If the current dose is the highest dose and the dose-assignment recommendation is "E", the study will continue to enroll new subjects at the current dose.
 - 5) Figure 1 is still applicable in the situation of subjects who have withdrawn due to some reason or more than 3 subjects enrolled in the current dose cohort. For example, if one of three enrolled subjects have withdrawn from the study due to some reasons, the i3+3 design will always appropriate to make a decision based on the data from the remaining 2 DLT evaluable subjects.

 \diamond Repeat the steps of 1) and 2) until the maximum sample size is reached.

After all of the subjects have enrolled and the observations have completed, isotonic regression will be used to select the MTD based on the observed DLT data and all safety data from all the dose levels^[19]. That is, if the toxicity probability of a dose is close to the target toxicity probability

after isotonic estimation, the dose will be selected as the MTD. In the case where the estimates of the toxicity probability of the two doses are consistent, if the estimate is less than the target toxicity probability, the higher dose will be selected as the MTD; if the estimate is greater than or equal to the target toxicity probability, the lower dose will be selected as the MTD. The MTD selection process can be implemented in the U-Design (https://udesign.laiyaconsulting.com/decision).

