APPENDIX 7 i3+3 DESIGN ALGORITHM

Similar to the 3+3 design^[18], the i3+3 is rule-based design, and it is also an interval-based design similar to mTPI¹⁹ The dose-assignment recommendation of the i3+3 design is based on the current observed DLT occurence and the relative position of the toxicity probability equivalence interval (EI). For example, if the observed DLT occurence at the current dose is below the lower limit of the equivalence interval, the i3+3 dose-assignment recommendation will be escalation "E". The specific i3+3 algorithm is as follows:

Suppose dose 'd' is the dose currently used to treat patients, 'n' is the number of patients who have been treated at dose 'd', and 'x' is the number of patients who have experienced DLTs at dose 'd'. The i3+3 dose-assignment recommendation will depend on two quantities x/n and (x-1)/n.

• If x/n is below the EI, escalate (E) and enroll patients at the next higher dose (d+1);

• If x/n is inside the EI, stay (S) and continue to enroll patients at the current dose d;

- If x/n is above the EI, there are two scenarios,
 - If (x-1)/n is below the EI, stay (S) and continue to enroll patients at the current dose d;
 - Else, de-escalate (D) and enroll patients at the next lower dose (d-1)

According to the above i3+3 algorithm and the preset EI, the i3+3 dose-assignment recommendation can be summarized in a decision table (Figure 1).

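### In the i3+3 phase a recommendation to escalate can rest on two DLT-evaluable subjects, because dropouts need not be replaced and no minimum number is set

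*Protocol*

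**What the plan says.** Protocol Section 4.1 waives replacement in the i3+3 phase: "If a subject terminates treatment due to non-DLT reasons during the first treatment cycle, there is no need to replace the subject". Replacement is provided for only in the titration phase, normally the 25 mg and 50 mg cohorts: "In the accelerated titration phase, a subject may be replaced if he/she 1) does not reach to 75% of the total planned dose", or stops the product for non-DLT reasons in the DLT window.

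The decision table counts evaluable subjects, not enrolled ones. The note to Figure 1 in Section 4.2 reads: "Each column represents (n) number of DLT evaluable subjects treated at the current dose". Item 5 of the same section states that "Figure 1 is still applicable in the situation of subjects who have withdrawn due to some reason". Its example is a cohort of three that loses one subject, and it concludes that "the i3+3 design will always appropriate to make a decision based on the data from the remaining 2 DLT evaluable subjects".

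Appendix 7 gives the escalation rule with no lower limit on n: "If x/n is below the EI, escalate (E) and enroll patients at the next higher dose (d+1". The equivalence interval (EI) is 16% to 30%.

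Other text assumes three completed subjects. Section 4.2 times the table decision with the words "After the three subjects in each cohort complete the DLT evaluation", and Section 4.1 times the SMC review in the same way.

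**The concern.** From 100 mg upward the design is meant to take each step on a cohort of three. Read together, the waiver of replacement, item 5 and Appendix 7 let an E recommendation arise from two evaluable subjects without a DLT. At a dose that is truly too toxic, a clean result is much likelier with two subjects than with three, so more subjects may be treated above the intended range.

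The text is also inconsistent. One sentence waits for three subjects to complete DLT evaluation, while item 5 decides on the two who remain. A site or the SMC cannot tell from the protocol whether three evaluable subjects are required.

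Appendix 8 does not settle the matter. It describes cohorts of three and mentions no non-evaluable subjects, so its comparison of i3+3 with 3+3 does not show how the design behaves when subjects are lost.

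**Working it through.** **1. What the rule gives at small n.** With 0 DLTs, x/n = 0, which is below 16%, so Appendix 7 returns E at 0/1, 0/2 and 0/3 alike. With one DLT, 1/1, 1/2 and 1/3 all lie above 30%, but (x-1)/n = 0 lies below 16%, so the result is S. For n of 3 or fewer, E therefore means no DLT observed.

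**2. Chance of a clean result.** P(0 DLT) = (1-p)^n.

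| True DLT rate p | n = 1 | n = 2 | n = 3 |
|---|---|---|---|
| 25% | 75.0% | 56.3% | 42.2% |
| 35% | 65.0% | 42.3% | 27.5% |
| 45% | 55.0% | 30.3% | 16.6% |

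**3. How often a first cohort falls short.** The protocol gives no non-evaluable rate, so 20% is assumed (range 10 to 30%).
- Fewer than three evaluable of three enrolled: 1 - 0.8^3 = 48.8% (27.1% at 10%, 65.7% at 30%).
- At most one evaluable: 0.2^3 + 3 × 0.8 × 0.2^2 = 10.4% (2.8% to 21.6%).
- If loss is independent of DLT, the chance of E from that cohort at p = 45% is 0.512 × 0.166 + 0.384 × 0.303 + 0.096 × 0.55 = 25.4%, against 16.6% with all three evaluable. At p = 35% it is 36.5% against 27.5%.

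**4. Reproducing Table 13.** The setting is a start at Dose 3, N = 30 and full evaluability. Two inputs are assumed: DU when Pr(p > 0.25) exceeds 0.95 under a Beta(1,1) prior, and no MTD whose isotonic estimate exceeds 0.30.

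| Scenario | Table 13, correct MTD | Reproduced |
|---|---|---|
| 1 | 0.42 | 0.440 |
| 2 | 0.608 | 0.598 |
| 3 | 0.788 | 0.796 |
| 4 | 0.665 | 0.683 |
| 5 | 0.702 | 0.703 |
| 6 | 0.849 | 0.849 |

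All are within 2 points. The 0.30 cap matters: without it Scenario 6 gives 0.647. One mismatch remains, the Scenario 6 toxicity rate (0.247 against the stated 0.277). The table's own counts also look like full evaluability: in Scenario 2, Dose 3, toxicities over subjects treated are 1.335/10.002 = 0.133, against a true rate of 0.13.

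**5. Adding non-evaluable subjects.** Every E is treated as followed. Two versions bracket the unknown: non-evaluability independent of DLT, and every DLT always counted.
- At 20%, about 40 to 71% of trials escalate at least once on fewer than three evaluable subjects, across Scenarios 1, 2, 3, 5 and 6 and both versions.
- With every DLT counted, the share at 10%, 20% and 30% non-evaluable is 27%, 43% and 54% in Scenario 1 and 36%, 57% and 68% in Scenario 2.
- At 20%, about 3 to 25% of trials do so from a dose whose true DLT rate exceeds 30% (Scenarios 1, 2, 5 and 6).

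**6. Effect of requiring three evaluable subjects for E**, topping up at the same dose, 20% non-evaluable. Mean subjects treated at doses with a true DLT rate above 30%:

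| Scenario | Version | As written | With minimum | Difference |
|---|---|---|---|---|
| 2 | independent | 4.5 | 3.0 | 1.5 |
| 5 | independent | 8.3 | 7.0 | 1.3 |
| 2 | every DLT counted | 2.4 | 1.7 | 0.7 |
| 5 | every DLT counted | 5.7 | 4.8 | 0.9 |

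In Scenarios 1 and 6 the reduction is about 0 to 1 subject. Correct MTD selection changes by about -4 to +2 points at 20%, and the loss reaches about 6 to 7 points at 30%, largest in the flat Scenario 3.

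**The case against.** The strongest reply is that the table does not decide. Under Section 4.1 the SMC weighs its output together with data from all treated subjects, including the non-evaluable ones. Enrollment is paused during review, and the SMC may ask for more subjects at the same dose. Section 7.4.1.3 repeats that it reviews the data before each dose step. Saying that replacement is not needed does not forbid it. Coping with dropouts is also one of the stated reasons for choosing i3+3 in Section 4.2.

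This stands in part. It means that the simulated escalation rates are an upper bound on what a cautious committee would do. It does not close the gap, because no passage obliges the SMC to hold when fewer than three are evaluable, and its charter is not shown.

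The reply is also right on three narrower matters:
- Item 5 illustrates two evaluable subjects only. Escalation on a single subject is inferred from Appendix 7, and the n = 1 column of Figure 1 cannot be checked.
- The non-evaluable rate has no source in the protocol. Entry requires a life expectancy of at least 12 weeks, and the first scheduled on-treatment scan (C2D28) falls after the 35-day window, so scheduled imaging would not remove subjects within it. Clinical progression still could.
- The high end of the 40 to 71% range comes from Scenario 3, where no dose exceeds a 28% DLT rate. The share escalating from a dose above 30% is the more telling figure.

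A reader might infer that the plan escalates automatically on one or two subjects, or that MTD selection is seriously harmed. The documents support neither. The first overlooks the SMC, and for the second the simulated effect of a minimum on selection is small and can go either way.

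**Conclusion.** The point holds in a limited form. The protocol expressly allows an E recommendation on 0/2, and by inference on 0/1. This conflicts with its own statements that three subjects first complete DLT evaluation, and Appendix 8 does not appear to cover the situation. Escalation on thin data is permitted, not mandated.

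The consequence is earlier exposure to higher doses on fewer observations, rather than a worse final MTD. The binomial figures depend only on the true rate and n. The simulated figures rest on an assumed 20% non-evaluable rate (range 10 to 30%), every E being followed, and the assumed DU rule and selection cap.

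The waiver of replacement names only subjects who stop treatment for non-DLT reasons in cycle 1. Whether other non-evaluable subjects in this phase are replaced, such as those below 75% of doses who continue, is not stated, which leaves the gap somewhat wider. This should be fixed as a cheap improvement; it does not undermine the design.

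**What to change.** Reconcile Section 4.1 with Section 4.2 item 5 (and the matching synopsis text) by stating that an E recommendation needs at least three DLT-evaluable subjects at the current dose. If there are fewer, the next subject or subjects enter at that dose until three are evaluable, within the existing maximum of 30, 36 or 42. S, D and DU may still be taken on fewer. The two sentences that refer to three subjects completing DLT evaluation should then say DLT-evaluable subjects.

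The cost is one amendment sentence with matching wording, no added subjects, slightly slower escalation, and the possible loss in correct MTD selection shown above. The minimum uses the plan's own cohort size, so it introduces no new design parameter.

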4.5. Dose Limiting Toxicity (DLT) Definition

A DLT is defined as the occurrence of any of the following toxic reactions that are considered to be causally related to 3D185 by the PI within the first 35 days after the first dose.

- 1. Hematological toxicity:
 - 1. Grade 4 hematologic toxicity;
 - 2. Grade 3 febrile neutropenia (defined as ANC < $1,000/\text{mm}^3$, a single temperature of >

38.3 \mathbb{C} or a sustained temperature of \geq 38 °C for more than 1 hour) or Grade 3 neutropenia

lasts for more than 7 days with or without drug intervention;

3. Grade 3 thrombocytopenia with bleeding or require to platelet transfusion;

- 2. Non-hematologic toxicity:
 - 4. Any Grade ≥ 3 non-hematologic toxicity (except the following conditions that can be controlled by symptomatic treatment within 48 hours: nausea, diarrhea, vomiting, and electrolyte imbalance [except serum phosphorus]; Grade 3 fatigue with duration ≤ 7 days; Grade 3 hypertension that can be self-resolved or controlled by drugs to below 140/90 mmHg or baseline level within 72 hours);
 - 5. Serum phosphorus ≥7 mg/dL that is unable to recover to < 7 mg/dL within 14 days after phosphorus removal;
 - 6. With liver metastasis or baseline transaminase abnormalities: ALT/AST > 8 × ULN; without liver metastasis or baseline transaminase abnormalities: ALT/AST > 5 × ULN ;
 - 7. 3D185-related AEs that resulted in dose interruption of 3D185 for \geq 7 days in the first treatment cycle.

If the DLT is clinically recovered to Grade 0-1 within 28 days, the subject can resume the treatment of 3D185. If the subject can resume treatment, the Investigator may refer to the provisions of Section 6.3 (Precautions and Dose Modifications) for dose modifications to the same dose or reduce by one dose level.

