5.4. Subject Study Completion and Withdrawal Criteria

5.4.1. Subject Study Completion

A subject will be considered to complete study if he/she has a valid PK profile and has not withdrawn from the study prior to the DLT evaluation period (first treatment cycle). A subject also will be considered to complete study if he/she discontinued study treatment due to a DLT with or without a valid PK profile.

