9.2.1. Analysis Population

Full Analysis Set (FAS)

The FAS will include all subjects who received 3D185 treatment in this study. The FAS will be the primary population for evaluating all efficacy, safety and subject characteristics.

DLT Analysis Set (DLT set)

The DLT set will include all subjects who received at least \geq 75% of the planned doses of treatment and completed the safety assessment during DLT evaluation period. The frequency and severity of DLT will be analyzed.

PK Analysis Set (PKS)

The PK set will include subjects who have received at least one dose and have at least once evaluable PK sample collection after administration.

PD Analysis Set (PD set)

The PD set will include subjects who have received at least one dose and have at least once serum phosphate level measurement (serum biochemistry) after administration.

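### The DLT-evaluable definition has no clause for subjects who had a DLT, so under Section 4.2 an early DLT can drop out of the i3+3 table, and the protocol gives three different (x, n) pairs

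*Protocol*

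**What the plan says.** **Evaluability.** Section 4.1, like the synopsis, reads: "The DLT evaluable subject is defined as the subject who received at least 75% of the planned doses of treatment". It adds that the safety assessment in the DLT period must be completed. Section 9.2.1 builds the analysis set the same way: "The DLT set will include all subjects who received at least" 75% of planned doses, again with the completed assessment. Having a DLT does not qualify a subject in any of these places.

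**Inputs to the decision table.** Three passages describe them differently.
- The operating steps in Section 4.2 determine the recommendation from Figure 1 "by using the safety data from the DLT evaluable subjects". Item 5 adds that, when one of three subjects has withdrawn for an unspecified reason, the design can "make a decision based on the data from the remaining 2 DLT evaluable subjects".
- The Figure 1 note takes n from evaluable subjects, but "each row represents (x) number of subjects with DLTs at the dose level", with no limit to evaluable ones.
- Appendix 7 says that n "is the number of patients who have been treated at dose" d, and that x counts all patients with DLTs there.

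**Related rules.** Section 4.5 lists "Grade 4 hematologic toxicity" as a DLT, and Section 6.3.3 lists any grade 4 toxicity for permanent discontinuation, with a case-by-case re-introduction exception. Section 4.1 makes a drug-related hold of more than 7 days a DLT. Section 5.4.1 does make an exception for DLTs, but only for study completion: a subject is "considered to complete study if he/she discontinued study treatment due to a DLT with or without a valid PK profile".

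**The concern.** A DLT is the event most likely to stop or interrupt dosing. A 75% dose requirement with no DLT exception therefore tends to remove the subjects the table exists to count. On the Section 4.2 wording the removed subject leaves both x and n, so the observed DLT rate is biased low and the recommendation moves toward escalation. The DLT-set rate is biased the same way, and DLT frequency is part of the primary endpoint.

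The three input definitions add a second problem. The same cohort can give opposite recommendations depending on the passage used. If x is kept while n shrinks, the table can be entered at a cell that cannot exist, such as x=2, n=1.

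The statistical analysis plan is not the place to settle this. The protocol itself fixes the definition, and it operates during enrolment.

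**Working it through.** **1. Who is lost.** The DLT window is one single dose plus a 28-day cycle (Section 4.1): 1 + 28 = 29 planned doses. 0.75 × 29 = 21.75, so 22 doses are needed.
- Lost: last dose on C1D20 or earlier (at most 21/29 = 72.4%), or a hold of more than 7 days wholly within Cycle 1 (8 missed, 21/29). In the second case the rule that declares the DLT also removes its subject.
- Kept: a 7-day hold (22/29 = 75.9%), a hold starting on or after C1D22, or a stop after the C1D21 dose.
- Counting only the 28 daily doses gives the same cut-offs: 21/28 = 75.0% kept, 20/28 = 71.4% lost.

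**2. Table readings.** Appendix 7 rule with the equivalence interval (16%, 30%), when the DLT subjects fall below 75%:

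| Observed | Appendix 7 | Section 4.2 text | Figure 1 note |
|---|---|---|---|
| 3 treated, 1 early DLT | 1/3: S | 0/2: E | 1/2: S |
| 3 treated, 2 early DLTs | 2/3: D | 0/1: E | 2/1: no such cell |
| 6 treated, 2 early DLTs | 2/6: D | 0/4: E | 2/4: D |

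**3. One cohort of three, exact.** Let p be the true DLT rate and f the share of DLT subjects who fall below 75% of doses. The protocol does not give f; the range 0.1 to 0.5 is assumed. With x and n both reduced, the table reads E when no DLT is retained and at least one subject is evaluable:

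P(E) = (1 − p(1 − f))³ − (pf)³

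For p = 0.25 and f = 0.5: 0.875³ − 0.125³ = 0.670 − 0.002 = 66.8%.

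| p | f=0 | f=0.1 | f=0.25 | f=0.5 |
|---|---|---|---|---|
| 25% | 42.2% | 46.5% | 53.6% | 66.8% |
| 45% | 16.6% | 21.1% | 28.9% | 45.4% |

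With x kept and only n reduced, P(x>n) = 3p²(1 − p)f² + p³(1 − (1 − f)³). At p = 0.25 and f = 0.5 this is 0.035 + 0.014 = 4.9%.

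**4. Whole trial, simulated.** Start at 100 mg, maximum 30 subjects, cohorts of 3, 4,000 trials per cell, no SMC override. The cells of Figure 1 were not available to this check, so DU is assumed to mean Pr(p > 0.25) > 0.95 under a Beta(1,1) prior with n ≥ 3. A dose is selectable only if its isotonic estimate is at most 30%. If n = 0, the decision is taken as D when x > 0 and S when x = 0.

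*Reproducing the protocol.* Table 13 gives over-MTD selection of 22.1% (Scenario 1) and 11.2% (Scenario 6). At f=0 the simulation gives 19 to 21% and 11%. The three rows per scenario describe the same procedure at f=0, so their small differences there are simulation noise.

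Over-MTD selection:

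| Reading | Scenario | f=0 | f=0.1 | f=0.25 | f=0.5 |
|---|---|---|---|---|---|
| x and n reduced in the table; isotonic on all treated | 1 | 21% | 25% | 31% | 39% |
| | 6 | 11% | 12% | 16% | 23% |
| x and n reduced; isotonic on the DLT set | 1 | 19% | 27% | 45% | 75% |
| | 6 | 11% | 16% | 29% | 62% |
| x kept, n reduced; isotonic on all treated | 1 | 20% | 20% | 18% | 19% |
| | 6 | 11% | 11% | 10% | 11% |

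On the first reading, mean subjects treated above the true MTD rise from 14 to 25 of 30 (Scenario 1) and from 14 to 24 (Scenario 6) at f=0.5. On the third reading selection does not worsen, but 24% and 25% of trials meet a cell with x>n at f=0.5, and about 3% at f=0.1. Repeating the simulation with separate code agreed to within about 2 points.

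**The case against.** **The bias depends on one wording.** The Figure 1 note and Appendix 7, which generates the table, both keep every DLT in x. This stands: the bias toward escalation arises under the Section 4.2 text. But that text is the operating instruction, and it conflicts with the other two. Strictly, x and n each have two definitions; it is the pair that has three.

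**Intent looks different.** Section 5.4.1 treats a subject who stops for a DLT as completing the study, so item 5 of Section 4.2 may not have had such a subject in mind. The no-replacement rule in Section 4.1 is likewise limited to non-DLT reasons. This is a fair reading of intent, but the evaluability definition does not say it.

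**Safeguards exist.** The SMC reviews all treated subjects, evaluable or not, and only takes the table into consideration. Section 9.4 summarises DLTs by dose cohort without limiting this to the DLT set, so an excluded DLT would still be reported. Both points stand, and the simulated figures are therefore table-only upper bounds. Neither safeguard corrects the stated recommendation or the DLT set.

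**The figures are sensitive to choices.** f has no source in the protocol. The 75% and 62% results require the isotonic estimate to use the DLT set alone, whereas Section 4.2 refers to observed DLT data and all safety data; the all-treated rows fit that text better. Scenarios 1 and 6 also start above their true MTD. On the all-treated reading at f=0/0.1/0.25/0.5, Scenario 2 gives 7/10/15/20% and Scenario 5 gives 7/9/11/13%: the same direction at lower levels.

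**Conclusion.** The concern holds and must be fixed. As written, an early DLT can make its own subject non-evaluable, and the Section 4.2 rule then reads 0/2 = E where 1/3 = S, or 0/1 = E where 2/3 = D, is the reading with every DLT counted.

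The dose counts, table cells and single-cohort formulas are exact given p and f. The whole-trial sizes rest on the assumed f, the assumed DU rule and the absence of SMC override. On the reading closest to the text for MTD selection (isotonic on all treated), over-MTD selection in Scenario 1 rises from 21% to between 25% and 39% for f from 0.1 to 0.5, and in Scenario 6 from 11% to between 12% and 23%. On the Figure 1 note's wording there is no such rise, but impossible cells appear.

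The defect lies in the pre-specified recommendation and the DLT set. It is not a prediction of what the SMC would decide or of the trial's result.

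**What to change.** In the synopsis, Section 4.1 and Section 9.2.1, define the DLT-evaluable subject and the DLT set as a treated subject who either
- had a DLT within the 35-day window, regardless of doses taken, or
- had no DLT, received at least 75% of planned doses and completed the safety assessment.

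State that this one set supplies x, n, the DLT rate and the isotonic estimate. Bring the Section 4.2 text (including item 5), the Figure 1 note and Appendix 7 into line with it.

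Two smaller points can be handled in the same edit. Replacement ground 1 in accelerated titration (under 75% of planned dose) also lacks a DLT exception; the effect is small, because replacement is optional and a Grade ≥ 2 related AE already triggers i3+3. The interruption DLT reads more than 7 days in Sections 4.1 and 6.3.2 but at least 7 days in Section 4.5, and these passages must be reconciled.

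Cost: one clause in three places and matching wording in Section 4.2, the Figure 1 note and Appendix 7. No extra patients or procedures.
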